8.2.4.6 Notifying the Clinical Sites NA

8.2.4.7 Reporting Pregnancy The investigator will be informed immediately of any pregnancy and will report all pregnancies within 24 hours to the NIAID Medical Officer (as described in Section 8.2.4.1) utilizing the SAE report form. This report is for tracking purposes only. All pregnancies that are identified during the study will be followed to conclusion and the outcome of each will be reported. The investigator will discuss with the participant and/or the treating physician the known possible risks of the investigational product(s) on the fetus. Monitoring of the participant will continue until the conclusion of the pregnancy, and a follow-up SAE report form detailing the outcome of the pregnancy will be submitted to the NIAID Medical Officer and Project Manager. If a participant is found to be pregnant they will be terminated from the study.

8.2.5 Non Serious Adverse Events (NSAES) Reporting

- **8.2.5.1** Notifying the Independent Safety Monitor The Principal Investigator will provide the Independent Safety Monitor with a listing of all AEs in a NIAID-provided standard format and timeline for review during planned protocol reviews. Individual or clusters of AEs may be reported expeditiously to the ISM either when specified by the ISM, or upon determination of the NIAID Medical Officer.
- **8.2.5.2 Notifying the Institutional Review Board** The Principal Investigator will ensure the timely dissemination of AE information to the IRB in accordance with applicable regulations and guidelines.

8.3 Protocol Deviations

The practices below are consistent with Good Clinical Practice (GCP ICH E6) Sections:

- Compliance with Protocol, sections 4.5.1, 4.5.2, and 4.5.3
- Quality Assurance and Quality Control, section 5.1.1
- Noncompliance sections 5.20.1, and 5.20.2

8.3.1 Protocol Deviation Definitions

- **8.3.1.1 Protocol Deviation** Any change, divergence, or departure from the study design or procedures of a research protocol that affects the participant's rights, safety, or well being and/or the completeness, accuracy and reliability of the study data constitutes a protocol violation. Changes or alterations in the conduct of the trial which do not have a major impact on the participant's rights, safety or well-being, or the completeness, accuracy and reliability of the study data are considered minor protocol deviations. The Principal Investigator is responsible for reporting protocol deviations to the IRB using the standard reporting form. As a result of deviations, corrective actions are to be developed by the site and implemented promptly.
- **8.3.1.2 Major Protocol Deviation** A protocol violation is a deviation from the IRB approved protocol that may affect the participant's rights, safety, or well being and/or the completeness, accuracy and reliability of the study data.

If the deviation meets any of the following criteria, it is considered a major protocol deviation (protocol violation). Example list is not exhaustive.

- 1. The deviation has harmed or posed a significant or substantive risk of harm to the research participant. Examples:
 - A research participant received the wrong treatment or incorrect dose.
 - A research participant met withdrawal criteria during the study but was not withdrawn.
- 2. The deviation compromises the scientific integrity of the data collected for the study. Examples:
 - A research participant was enrolled but does not meet the protocol's eligibility criteria.
 - Failure to treat research participants per protocol procedures that specifically relate to primary efficacy outcomes. (if it involves patient safety it meets the first category above)
 - Changing the protocol without prior IRB approval.
 - Inadvertent loss of samples or data.
- 3. The deviation is a willful or knowing breach of human participant protection regulations, policies, or procedures on the part of the investigator(s). Examples:
 - Failure to obtain informed consent prior to initiation of study-related Procedures
 - Use of outdated or incorrect consent forms
 - Falsifying research or medical records
 - Performing tests or procedures beyond the individual's professional scope or privilege status (credentialing)
- 4. The deviation involves a serious or continuing noncompliance with federal, state, local or institutional human participant protection regulations, policies, or procedures. Examples:
 - Working under an expired professional license or certification
 - Failure to follow federal and/or local regulations, and intramural research
 - Repeated minor deviations.
- 5. The deviation is inconsistent with the NIH Human Research Protection Program's research, medical, and ethical principles. Examples:
 - A breach of confidentiality.
 - Inadequate or improper informed consent procedure.

8.3.1.3 Non-Major Protocol Deviation A non-major protocol deviation is any change, divergence, or departure from the study design or procedures of a research protocol that has not been approved by the IRB and which DOES NOT have a major impact on the participant's rights, safety or well-being, or the completeness, accuracy and reliability of the study data.

8.3.2 Reporting Protocol Deviations

Upon determination that a protocol deviation has occurred, the study staff will a) notify the Principal Investigator, b) notify the NIAID Project Manager(refer to investigator's signature page for contact information) and c) will complete the Protocol Deviation form (Appendix 4). NIAID may request discussion with the Principal Investigator and the Independent Safety Monitor to determine the effect of the protocol deviation on the study participant and his/her further study participation, the effect of the protocol deviation on the overall study and corrective actions. The Principal Investigator will complete and sign the Protocol Deviation form and submit it to the NIAID Medical Officer and Project Manager, to the Independent Safety Monitor and to the site IRB, per IRB regulations. Major protocol deviations will be reported to the ISM by the NIAID Medical Officer. The IND sponsor will be responsible for notifying the FDA.

All study staff be educated about the adverse event reporting policy, and will be instructed to notify an investigator if an event occurs.

9 SAMPLE SIZE CALCULATIONS AND STATISTICAL PLAN

9.1 Sample Size and Power Calculations

As the hypothesis regarding Treg induction and clonal tolerance can only be defined among those individuals who achieve desensitization and go on to DBPCFC3, the analysis will be per protocol for those participants who complete both post treatment challenges. The difference in the proportion of Treg will be compared between the groups using Students t test for comparison of means. Because we are expecting the primary outcome variable (difference in the proportion of Treg) to be log-normally distributed, we plan to carry out the t test on the log transformed variable. We will be powered at the expected effect on Treg if as few as six individuals (20% clinical effect and 10% dropout) who complete the protocol achieve our defined measure of at least partial clinical tolerance. Table 15.6 shows power calculations around these assumptions using a two sided t test at an alpha level of 0.05.

The sample size selected is 30 active treatment and 10 placebo treatment. We are applying the following assumptions for our power analysis (see Figure 15.5 for schema of assumptions).

- Approximately 27% of the Active Treatment group (8/30) will achieve Partial Tolerance (ED at DBPCFC3 <4430 mg but ≥430 mg AND >10-fold more than at DBPCFC1) or Full Tolerance (no reaction at DBPCFC3).
- The comparison of interest is between the combined Tolerance/Partial Tolerance and Active Treatment Failure groups who complete DBPCFC3.
- Those who fail to become desensitized after active treatment and those who receive placebo treatment are not fully informative for the primary endpoint and are therefore excluded for the per protocol analysis.
- The difference from baseline to the end of maintenance therapy in the mean proportion of induced Treg (CD45RA- CD25++ FoxP3++ of CD4+ T cells) between the Tolerance/Partial Tolerance and Treatment Failure groups will be 1.5 times the standard deviation.

The placebo group will be used primarily to assess whether and to what extent there are more AEs associated with treatment. However, we will be able to also perform an intention to treat analysis of the primary outcome (difference in Treg proportion at the second blood draw from baseline) including the Placebo group. There is no expected effect on Treg in the placebo group and as above the comparison of interest is of outcomes within the actively treated participants who complete DBPCFC3. Estimating that 27% of active arm treatment achieve significant tolerance (n=8; see Figure 15.5) and that all Placebo group participants are defined as Treatment Failures after DBPCFC2 (n=10) and that the remaining Active Treatment participants will lose tolerance during avoidance (n=14), then we will have 100% power at an α level of 0.05 to detect the expected 1.5 X SD difference.

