2 OBJECTIVES

2.1 Primary Objective(s)

To determine whether PN OIT induced clinical tolerance in the context of food allergy is significantly associated with the expansion of a specific regulatory T cell subset (CD45RA- CD25++ FoxP3++) that is thought to be inducible in the gut-associated lymphoid compartment and associated with immunological tolerance.

We will measure the change from baseline of induced Treg cells as a frequency of total CD4 T cells during active treatment and compare that between participants who achieve significant clinical tolerance (Tolerance and Partial Tolerance Groups as defined below) and those who do not (Treatment Failure Group).

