3.1 Study Endpoints

3.1.1 Primary Endpoint(s)

The difference in the proportion of induced Treg cells (CD45RA- CD25++ FoxP3++ of CD4+ T cells) from baseline to the end of maintenance therapy.

CONFIDENTIAL

Clinical outcomes will be defined as follows:

- Treatment Failure: Failure to achieve the minimum maintenance dose (600 mg) of peanut protein by 12 months, or an ED <1443 mg at DBPCFC2, or ED at DBPCFC3 <443 mg OR <10-fold more than at DBPCFC1.
- Partial Tolerance: ED at DBPCFC3 <4430 mg but ≥430 mg AND >10-fold more than at DBPCFC1.
- Tolerance: Ingestion of 4430 mg of peanut protein at DBPCFC3 without symptoms.

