9.2.4 Study Endpoints

9.2.4.1 Primary Endpoint The difference in the proportion of induced Treg cells (CD45RA- CD25++ FoxP3++ of CD4+ T cells) from baseline to the end of maintenance therapy.

9.2.4.1.1 Clinical outcomes will be defined as follows:

- Treatment Failure: Failure to achieve the minimum maintenance dose (600 mg) of peanut protein by 12 months, or an ED <1443 mg at DBPCFC2, or ED at DBPCFC3 <430 mg OR <10-fold more than at DBPCFC1.
- Partial Tolerance: ED at DBPCFC3 <4430 mg but ≥430 mg AND >10-fold more than at DBPCFC1.
- Tolerance: Ingestion of 4430 mg of peanut protein at DBPCFC3 without symptoms.

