15.6 Power Analysis for Comparison of Tolerance and Treatment Failure groups

Clinical Effect	Tol	Fail	power	Tol	Fail	power
33%	10	12	0.97	9	10	0.95
27%	8	14	0.96	7	12	0.93
23%	7	15	0.95	6	13	0.92

Treg difference = 1.75σ

Clinical Effect	Tol	Fail	power	Tol	Fail	power
33%	10	12	0.91	9	10	0.87
27%	8	14	0.90	7	12	0.84
23%	7	15	0.88	6	13	0.82

Treg difference = 1.5σ

Clinical Effect	Tol	Fail	power	Tol	Fail	power
33%	10	12	0.79	9	10	0.73
27%	8	14	0.77	7	12	0.70
23%	7	15	0.74	6	13	0.67

Treg difference = 1.25σ

Power calculations for varying clinical effect and Treg effect sizes using a two sided t test (α =0.05). The difference in induced Treg proportion between combined Partial Tolerance and Tolerance groups (Tol) versus the Active Treatment Failure group (Fail) is the primary endpoint. We are hypothesizing a difference in Treg proportion (mean of log-transformed data) of 1.5 σ (based on Jones, et al. [?]). Left side of table without drop out; right side with drop out (10% of the estimated 22 avoiding between DBPCFC2 and DBPCFC3).

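### Section 9.1 puts the primary t test on the log of a change from baseline, which is undefined when the Treg proportion does not rise, and the plan does not settle the scale of the variable or of the 1.5 SD effect

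*Combined protocol and SAP*

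**What the plan says.** The primary objective (2.1) is stated as a change over time: "We will measure the change from baseline of induced Treg cells as a frequency of total CD4 T cells during active treatment". The primary endpoint in 9.2.4 is "The difference in the proportion of induced Treg cells", and both 9.2.4 and 3.1.1 take it "from baseline to the end of maintenance therapy".

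Section 9.1 compares this between the combined Tolerance/Partial Tolerance group and the Treatment Failure group by Student's t test. It says of the primary outcome variable that the sponsor expects the "difference in the proportion of Treg) to be log-normally distributed, we plan to carry out the t test on the log transformed variable".

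The effect size appears twice. The fourth power assumption in 9.1 sets at 1.5 standard deviations "The difference from baseline to the end of maintenance therapy in the mean proportion of induced Treg", compared between the two groups, and mentions no log. The note to table 15.6 says the sponsor is "hypothesizing a difference in Treg proportion (mean of log-transformed data"), again with 1.5 SD.

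Section 9.1 also describes an "intention to treat analysis of the primary outcome (difference in Treg proportion at the second blood draw from baseline) including the Placebo group". It does not restate the log there.

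**The concern.** A log-normal variable is strictly positive. A change from baseline is not: it is zero for a participant whose induced Treg proportion is unchanged and negative for one whose proportion falls. The distributional assumption therefore cannot hold for the variable as defined, and the planned transformation fails on valid data.

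This is the sole primary test, on about 22 people. On the literal text, one per-protocol participant without a rise means the test cannot be run on everyone it was planned for. Someone must then decide whether to drop the value, add a constant, abandon the log or switch to a ratio, possibly after seeing which group holds the problem values. Dropping is the most harmful choice, because it removes participants according to the outcome being tested. Under the trial's hypothesis, those without Treg expansion should mostly be treatment failures.

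**Working it through.** **1. The plan's own power figures.** Inputs from 9.1 and 15.6: two-sided t test, α = 0.05, d = 1.5, group sizes as tabulated. Power comes from the noncentral t distribution with df = n1 + n2 − 2 and noncentrality d·√(n1·n2/(n1 + n2)).

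- 8 v 14: df = 20, noncentrality 1.5·√(112/22) = 3.38, power 0.896 (table: 0.90).
- 7 v 12: df = 17, noncentrality 1.5·√(84/19) = 3.15, power 0.844 (table: 0.84).
- 6 v 13: df = 17, noncentrality 1.5·√(78/19) = 3.04, power 0.817 (table: 0.82).

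All 18 cells of table 15.6 reproduce to two decimals, so the arithmetic is right. Because the effect is in SD units, the table cannot show which scale the SD belongs to.

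**2. Which quantity is logged.** Write p0 for the baseline proportion and p1 for the end-of-maintenance proportion.

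- Literal 9.1, with the endpoint of 3.1.1 and 9.2.4: log(p1 − p0). This exists only if p1 > p0.
- Reading allowed by the note to 15.6: log(p1) − log(p0). This exists whenever both proportions are positive, and it is negative when the proportion falls.
- Fourth assumption in 9.1: 1.5 SD with no log. It does not favour the log-ratio and fits an untransformed change at least as well.

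Two statisticians following this text could run different primary tests.

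**3. Whether another section supplies a rule.** Section 9.2.1 covers descriptive summaries only. Section 9.2.5 excludes missing or spurious immune data, and a validly measured fall is neither. Section 9.4 requires an amendment for changes to principal features, but it does not say what to do with a non-positive change, nor that the choice must precede sight of the data. No offset or alternative transformation appears anywhere.

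**4. How often the literal test would fail.** The documents give no distribution for the change, so the per-participant chance q of a non-positive change is an assumption. It is taken here as equal and independent across participants. The chance of at least one undefined value among n is 1 − (1 − q)^n.

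| q | n = 22 (no dropout) | n = 19 (table 15.6 with dropout) |
|---|---|---|
| 5% | 1 − 0.95^22 = 68% | 1 − 0.95^19 = 62% |
| 10% | 1 − 0.90^22 = 90% | 1 − 0.90^19 = 86% |
| 20% | 1 − 0.80^22 = 99% | 1 − 0.80^19 = 99% |

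**5. After the fix.** If the 1.5 SD applies to log(p1) − log(p0), step 1 applies as it stands: 0.896 for 8 v 14 and 0.817 for 6 v 13.

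**The case against.** The strongest reply is that the sponsor plainly meant something workable. Only a positive quantity can be log-normal, the note to 15.6 speaks of means of log-transformed data, and the same note uses the word difference for the between-group contrast, so the term is used loosely. On that view this is a matter of wording.

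Part of this stands. The log-ratio reading is available, and under it the test runs on all positive proportions. But 9.1 describes a variable with a distribution across participants, which a between-group contrast is not, and the endpoint sections define that variable as a change from baseline. The plan never adopts the log-ratio.

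A reader might infer three stronger things that the documents do not support:

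- **That the primary test will lose a stated amount of power.** Any such figure needs an assumed distribution for the change and a rule for the undefined values, and the plan gives neither. The answer moves with both choices. The per-protocol failures are also people who were desensitised and completed DBPCFC3, and nothing says their mean change is zero.
- **That a known share of placebo values would be undefined in the intention-to-treat analysis.** Section 9.1 does say "There is no expected effect on Treg in the placebo group". A count would still need the same transformation to be used there and placebo changes to be symmetric about zero, and neither is stated.
- **That table 15.6 is wrong.** It reproduces.

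**Conclusion.** The point holds, and the text is wrong as written rather than merely short on detail: a stated rule for the primary test fails on valid observations, and nothing in the plan repairs it. The scale of the primary variable and of the 1.5 SD is also left open between 9.1 and 15.6.

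The failure is certain for any participant without a rise. How many there will be is unknown. The 68%, 90% and 99% figures rest on assumed chances of 5%, 10% and 20% per participant and on independence. They show how little it takes to trigger the problem and do not predict this trial. If a log-ratio was intended and the 1.5 SD belongs to it, no power is lost. The documents do not show whether that condition is met.

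**What to change.** Before outcome data are examined:

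- In 9.1, define the primary variable as log(end-of-maintenance proportion) minus log(baseline proportion), and use the same scale in the intention-to-treat analysis.
- Add a short rule for a measured proportion of zero, should one occur.
- Check the source study cited in 15.6 to confirm that the 1.5 SD applies on the log-ratio scale. If it does not, restate the effect size, and the power that follows from it, in 9.1 and 15.6.

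The cost is one sentence, one short rule and one check of the source. The baseline and end-of-maintenance samples are already planned, so no new samples or participants are needed. The downside is that results read as fold change and not as percentage-point change.

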9.2.2 Study Participant Populations

As described above, the per protocol sample will consist of all active treatment participants completing DBPCFC3.

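### The failure group in the primary Treg t test is not consistently defined: participants who fail DBPCFC2 are Treatment Failures by definition, excluded in 9.1, and not clearly excluded in 9.2.2 or 9.2.5

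*Combined protocol and SAP*

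**What the plan says.** Section 2.1 sets the comparison: change in induced Treg in participants who reach Tolerance or Partial Tolerance "and those who do not (Treatment Failure Group". Sections 3.1.1 and 9.2.4.1.1 give several routes into Treatment Failure: not reaching 600 mg, "or an ED <1443 mg at DBPCFC2", or an insufficient ED at DBPCFC3. Section 5.6.1 repeats the DBPCFC2 route for active participants.

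These statements bear on who enters the primary test:

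- **9.1** limits it to participants who complete both post-treatment challenges and contrasts the tolerant groups with active failures who complete DBPCFC3. It then says "Those who fail to become desensitized after active treatment and those who receive placebo treatment are not fully informative for the primary endpoint", and excludes both kinds.
- **9.2.2** refers back to the earlier description and states that "the per protocol sample will consist of all active treatment participants completing DBPCFC3". It does not repeat a desensitization condition.
- **9.2.5**, for a primary outcome that it calls Tolerance, takes everyone who completes the modified rush visit. It drops missing or spurious immune data.
- **The synopsis, 9.1 and Table 15.6** all use 8 tolerant v 14 failures as the base case.

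On the test itself, "we plan to carry out the t test on the log transformed variable", and the difference "between the Tolerance/Partial Tolerance and Treatment Failure groups will be 1.5 times the standard deviation".

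**The concern.** A participant who fails DBPCFC2 belongs to the comparator under the outcome definitions and is outside it under 9.1. Under a literal reading of 9.2.2 that participant is back inside if DBPCFC3 is completed.

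Assignment is unblinded after DBPCFC2 (7.1). Attendance at DBPCFC3, and the choice between these readings, therefore come after the allocation and the DBPCFC2 result are known. With about 8 people expected in the tolerant group, moving one of them matters.

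The 9.1 set is also selected on an outcome observed after treatment began, and that outcome may itself be related to Treg change. The secondary mechanistic endpoints in 3.1.2 that compare clinical outcome groups inherit the same definitions.

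**Working it through.** **1. Do DBPCFC2 failures go on to DBPCFC3?** Section 5.6.1 only recommends a return to strict avoidance, and avoidance is also the condition that precedes DBPCFC3. Section 7.4.7 sends participants to DBPCFC3 without restriction. Failing DBPCFC2 is not among the withdrawal criteria (4.3) or the individual stopping rules (8.1.2). The question is left open.

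**2. Can one person meet two definitions?** The thresholds correspond to cumulative doses, so ED is read as cumulative here. From the steps in 7.7.1:
- DBPCFC1: 3, 13, 43, 143, 443 mg.
- DBPCFC2: the same, then 1443 and 4443 mg.
- DBPCFC3: 30, 130, 430, 1430, 4430 mg.

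Take EDs of 13, 443 and 430 mg at the three challenges. Since 443 < 1443, this is Treatment Failure. Since 430 ≤ 430 < 4430 and 430/13 = 33.1 > 10, it is also Partial Tolerance under 9.2.4.1.1. (Section 3.1.1 prints 443 mg rather than 430 mg as the DBPCFC3 failure limit, so there the same person fails on DBPCFC3 too and still meets Partial Tolerance.) Tolerance likewise has no DBPCFC2 condition.

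**3. Counts.** "The sample size selected is 30 active treatment and 10 placebo treatment". Section 15.5 expects 75% desensitized: 30 × 0.75 = 22.5, used as 22. Failures among them: 22 − 8 = 14. Non-desensitized active participants: 30 − 22 = 8. With the 10% dropout in Table 15.6, 8 v 14 becomes 7 v 12.

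Adding all 8 gives 14 + 8 = 22. Under 9.2.2 that would need every one of them to complete DBPCFC3 and to have an end-of-maintenance sample. For an intermediate range, assume that the 10–18% adverse-reaction dropout cited in 1.5.2 applies (30 × 0.10 = 3; 30 × 0.18 = 5.4, about 5), that it falls wholly among these 8, and that the rest are sampled and challenged. Then 3 to 5 are added, giving an arm of 17 to 19.

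**4. Power.** Two-sided t test, α = 0.05, from the noncentral t distribution with df = n1 + n2 − 2 and noncentrality d·√(n1·n2/(n1 + n2)). For 8 v 14 at d = 1.5 the noncentrality is 1.5 × √(112/22) = 3.38 and power is 0.896, against 0.90 in Table 15.6. For 7 v 12 it is 0.844, against 0.84. All 18 cells of the table reproduce within 0.01.

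| Tolerant v failure | Power at 1.5 SD |
|---|---|
| 8 v 14 | 0.896 |
| 8 v 17 | 0.918 |
| 8 v 19 | 0.928 |
| 8 v 22 | 0.939 |

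**5. If the added participants differ from the other failures.** Suppose k are added and their mean Treg change lies 0.75 SD toward the tolerant group (halfway) or 0.75 SD away from it. Both are assumptions. The mean difference is 1.5 ∓ 0.75k/(14 + k). Power is from 100,000 simulated trials per case.

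| k | Halfway toward: difference, power | Away: difference, power |
|---|---|---|
| 3 | 1.37 SD, 0.85 | 1.63 SD, 0.95 |
| 5 | 1.30 SD, 0.82 | 1.70 SD, 0.97 |
| 8 | 1.23 SD, 0.79 | 1.77 SD, 0.98 |

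**6. The intention-to-treat analysis in 9.1.** It counts 8 + 10 + 14 = 32 of 40. The missing 8 are the same non-desensitized active participants, although placebo participants are counted as failures after DBPCFC2.

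**The case against.** Section 9.2.2 points back to 9.1, and 9.1 describes those who go on to DBPCFC3 as having achieved desensitization. Read together, the two give one population. The planned comparator is also stated: active failures who complete DBPCFC3, numbering 14 wherever the base case appears. Section 5.6.1 labels a DBPCFC2 failure a treatment failure and later treats the outcome categories as exclusive, which would settle the 13/443/430 mg case. Section 9.4 requires an amendment for changes to principal features, so the population is not freely open to later choice. Section 9.1 also offers an intention-to-treat analysis.

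Much of this stands, and it rules out several stronger readings that a reader might infer:

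- **That 9.1 and 9.2.2 flatly contradict each other.** The conflict is conditional on a DBPCFC2 failure completing DBPCFC3.
- **That the plan leaves the arm anywhere from 14 to 22.** The planned figure is 14, it falls to 12 with dropout, and no section gives 22 as a failure-arm size. The documents' own 22 is the total of DBPCFC3 completers, 8 + 14.
- **That the trial loses power.** At a fixed effect, a larger failure arm raises it.
- **That the exclusion favors the hypothesis.** If DBPCFC2 failures have the lowest Treg changes, dropping them narrows the contrast. If theirs lie between the groups, dropping them widens it. The documents do not say which.

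What the objection does not remove: no section keeps DBPCFC2 failures out of DBPCFC3; the definitions in 9.2.4.1.1 overlap and carry no precedence rule; 9.2.5 states a different population; and the intention-to-treat count leaves out the same 8 people. Section 9.4 governs changes to the plan, not a choice between readings already in it. On 9.2.5, participants without an end-of-maintenance sample would leave the Treg test as missing, but DBPCFC2 failures who have that sample would stay.

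**Conclusion.** The comparator of the primary t test is not consistently defined, and this should be fixed before analysis. It is a matter of who is compared, not of sample size. The planned contrast is 8 v 14 (7 v 12 with dropout). A literal reading of 9.2.2 could bring in some of the 8 non-desensitized active participants: 3 to 5 under the borrowed dropout range, 8 only as a ceiling.

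Nominal power stays between 0.90 and 0.94 if the added participants resemble the other failures. Under the illustrative shifts above it runs from 0.79 to 0.98, so the effect of the choice could go either way.

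The conclusion rests on reading ED as cumulative dose and on treating ED ≥1443 mg at DBPCFC2 as desensitized. The second is an inference from the plan's own failure threshold: 9.1 gives no individual definition, and 2.2.1 defines desensitization through group medians and accidental-reaction frequency.

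**What to change.** (a) In 3.1.1 and 9.2.4.1.1, state that Tolerance and Partial Tolerance require that no Treatment Failure criterion was met earlier. Align the 443 and 430 mg limits in the same edit.

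(b) Put one primary population in 9.1, 9.2.2 and 9.2.5: active participants with ED ≥1443 mg at DBPCFC2 who complete DBPCFC3. This matches 9.1 and Table 15.6. In 2.1, name the comparator as those who lost tolerance at DBPCFC3, separate from those who failed desensitization. Reconcile 5.6.1, 7.4.7 and 9.1 on whether DBPCFC2 failures go on to DBPCFC3; which way is for the investigators to decide.

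(c) Pre-specify one sensitivity t test that adds to the failure arm the DBPCFC2 failures with baseline and end-of-maintenance Treg values. Section 7.4.4 places the second sample before DBPCFC2, so participants who reach that challenge should already have it.

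Cost: wording in five or six sections and one extra t test. No added visits, samples or participants.

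### The 100% power in Section 9.1 for the analysis including placebo is about 94% on its own inputs, and that analysis is not intention to treat

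*Combined protocol and SAP*

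**What the plan says.** Section 9.1 plans 40 participants: "The sample size selected is 30 active treatment and 10 placebo treatment". The primary comparison is of Treg change between tolerant or partially tolerant participants and treatment failures, among actively treated participants who complete DBPCFC3. Placebo is left out of it: "those who receive placebo treatment are not fully informative for the primary endpoint and are therefore excluded for the per protocol analysis". Section 9.2.2 agrees: "the per protocol sample will consist of all active treatment participants completing DBPCFC3".

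The last paragraph of Section 9.1 then says "we will be able to also perform an intention to treat analysis of the primary outcome", with the placebo group included. For its power it takes 27% of the active arm as tolerant (n=8). On the control arm it supposes: "all Placebo group participants are defined as Treatment Failures after DBPCFC2 (n=10"). For the other people given peanut flour, its supposition reads: "the remaining Active Treatment participants will lose tolerance during avoidance (n=14"). The power figure drawn from these counts is: "then we will have 100% power at an α level of 0.05 to detect the expected 1.5 X SD difference". The same paragraph says that "the comparison of interest is of outcomes within the actively treated participants who complete DBPCFC3".

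**The concern.** There are two problems.

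- **The figure.** Table 15.6 gives 0.90 for 8 versus 14 at 1.5 SD. Adding 10 participants to the larger group leaves the smaller one at 8, and the smaller group dominates the standard error. Power should rise a little, not to certainty.
- **The label.** Intention to treat means that randomised participants are compared by assigned arm. The counts given are of outcome groups, with placebo and failing active participants on the same side.

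A reader who takes both statements at face value would believe that the trial has a near-certain test of the randomised comparison on Treg. The plan describes no such test.

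**Working it through.** **Inputs.** The counts of 8, 14 and 10, the 1.5 SD difference and alpha 0.05 come from Section 9.1. The two-sided t test is stated in Section 9.1 and under Table 15.6. The paragraph on the added analysis does not restate sidedness, so two-sided is carried over.

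**Formula.** For group sizes n1 and n2 and a difference of d standard deviations, the t statistic is noncentral t with n1 + n2 − 2 degrees of freedom and noncentrality d / √(1/n1 + 1/n2). Power is the probability of exceeding the two-sided 5% critical value.

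**Reproducing the plan's own table.** For 8 versus 14 at 1.5 SD, noncentrality is 1.5 / √(1/8 + 1/14) = 3.38 on 20 df, and power is 0.896 (table: 0.90). All 18 cells of Table 15.6 are reproduced, with a largest gap of 0.005. This is therefore the plan's own method.

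**The added analysis.** The failures number 14 + 10 = 24. Noncentrality is 1.5 / √(1/8 + 1/24) = 3.67 on 30 df, and power is **0.945**. A simulation of 200,000 trials gives 0.944.

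**Could another reading give 100%?**

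| Reading, at 1.5 SD | Power |
|---|---|
| 8 vs 24, two-sided t | 0.945 |
| 8 vs 24, two-sided normal approximation | 0.957 |
| 8 vs 24, one-sided t | 0.974 |
| 8 vs 32 (all 40 counted), two-sided t | 0.959 |
| 30 vs 10 by arm, two-sided t | 0.979 |
| 8 vs unlimited failures, two-sided | 0.989 |

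The last row is Φ(1.5 × √8 − 1.96) = Φ(2.28), the ceiling for a two-sided test with 8 tolerant participants. The 30 versus 10 row applies the 1.5 SD to a contrast for which Section 9.1 does not state it. Rounding does not explain the figure either: with 8 versus 24, power of 99.5% needs about 1.91 SD, above the largest effect in Table 15.6 (1.75 SD).

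**Who is counted.** 8 + 14 + 10 = 32 of the 40 randomised. The other 30 − 8 − 14 = 8 active participants appear in neither group.

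**What a comparison by arm would look like.** Suppose that 8 of 30 active participants shift by 1.5 SD and nobody else shifts. Section 9.1 expects no placebo effect; no shift in the remaining active participants is an assumption made here. The mean difference between arms is 8/30 × 1.5 = 0.4 SD. Power for 30 versus 10 is then about 15% if the extra spread in the active arm is allowed for, and about 19% if it is not. A general Treg rise on treatment would increase it.

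**If placebo is pooled with the failures.** Suppose that treatment raised Treg equally in all active participants, whether or not they became tolerant. There would be no link with tolerance, but the pooled test would still compare active participants with a partly placebo group. In simulation, assumed shifts of 0.5, 1.0, 1.5 and 2.0 SD give rejection rates of 7%, 13%, 19% and 27% for 8 versus 14 + 10, and of 6%, 9%, 12% and 15% for 8 versus 22 + 10. The active-only test stays at 5%. The documents give no value for this shift.

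**The case against.** The best case on the other side is that this matters little. The analysis is supplementary, 94% is still high, no design choice depends on the sentence, and the paragraph itself places the comparison of interest within the active arm. All of that stands and limits the weight of the point. It does not make the figure right.

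Second, Section 9.1 never writes out which two groups are tested, so pooling placebo with failures is an inference. That also stands, although placebo participants are expressly classed as failures and the counts given are outcome counts. The power conclusion does not depend on it, since a test by arm at 1.5 SD gives 0.979, not 1.00.

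Third, Table 15.6's dropout rows could be applied, giving 0.91 (7 versus 12 + 10) or 0.88 (6 versus 13 + 10). But that dropout falls between DBPCFC2 and DBPCFC3, after the end-of-maintenance blood draw, and the plan does not say whether such participants would leave this analysis. The second figure also moves from the 27% to the 23% clinical effect. These are side figures and the conclusion does not use them.

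Fourth, the pooling rates rest on shifts chosen for illustration. They show a direction, not an expected size.

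**Conclusion.** The concern holds on both counts. On the stated counts, with 1.5 SD and a two-sided 5% t test, power is about 94%, not 100%. It is about 96% if the 8 uncounted active participants are added as failures. No reading tried reaches 100%, and 98.9% is the two-sided ceiling with 8 tolerant participants. The type II error is therefore about 5.5%, where the plan implies none.

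The label is also wrong: the groups counted are defined by outcome after randomisation and leave out 8 of the 40 randomised. The caution about pooling is conditional on pooling being done and on a general Treg shift among active participants, and it bears only on how such a result is described.

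The active-only primary analysis, its 0.90 power and the sample size are unaffected. The correction should be made, but it is a small one.

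**What to change.** In the last paragraph of Section 9.1:

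- Replace the 100% with about 94%, and state the counts it refers to (8 versus 14 + 10, two-sided t test). If all 40 are meant to be counted, state 8 versus 32 and about 96%. Deleting the power sentence would also do.
- Remove the intention-to-treat label from the comparison of outcome groups.
- If a pooled result will be reported, add one line saying that the inference about tolerance rests on the active-only comparison already named in that section.

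Optionally, if a placebo comparison of Treg is wanted, compare the randomised arms and present the result as a test of treatment effect on Treg, not of tolerance. Call it a by-arm available-case analysis unless all 40 are included with a stated method for missing data, and give it its own power statement.

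The cost is one number and one label in one paragraph. Sample size, visits and the primary analysis do not change; the stated power becomes slightly less favourable.
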